10.9. Appendix 9: Proposed Chronology of Procedures

For the procedures described below, where multiple procedures are scheduled at the same timepoint(s) relative to dosing, the following chronology of events should be adhered to:

- 12-lead ECG: obtain prior to blood samples, and prior to dosing (except for post-dose collection) (see [Section 8.2.4](#));
- Vital Signs (BP, PR): obtain prior to obtaining blood samples and prior to dosing (except for post-dose collection) (see [Section 8.2.3](#));
- Fasting blood samples (for safety [see [Section 8.2.6](#)], PK [see [Section 8.5](#)], **CC1** [REDACTED] after assessment of 12-lead ECG and vital signs but prior to dosing (If an IV catheter is utilized for blood sample collections, ECGs and vital sign assessments [PR and BP] should be collected prior to the insertion of the catheter.);
CC1 [REDACTED]
- Post-dose PK blood collection to occur approximately 4 hours post-dose (see [Section 8.5](#)): if collection time coincides with time of a meal/snack, these blood samples should be collected just prior to the meal/snack;
- Other pre-dose procedures: obtain sample/perform procedure as close as possible to the scheduled time, but may be obtained before or after blood sample collection(s);
- Dosing: must occur in the morning with food and in the evening with food; and where applicable, after any pre-dose blood sample collection(s).

10.10. Appendix 10: Abbreviations

The following is a list of abbreviations that may be used in the protocol.

Abbreviation	Term
%CV	percent coefficients of variance
Abs	absolute
AE	adverse event
ALT	alanine aminotransferase
AST	aspartate aminotransferase
AUC	area under the concentration-time curve
AV	atrioventricular
BCRP	breast cancer resistance protein
β-hCG	β-human chorionic gonadotropin
BID	twice a day
BMI	body mass index
BP	blood pressure
bpm	beats per minute
BUN	blood urea nitrogen
cAMP	cyclic adenosine monophosphate
CCI	[REDACTED]
CFR	Code of Federal Regulations
CIOMS	Council for International Organizations of Medical Sciences
CK	creatine kinase
CKD-EPI	Chronic Kidney Disease Epidemiology Collaboration
CL	total clearance of drug from eg, plasma
CCI	[REDACTED]
C _{max}	maximum observed concentration
CONSORT	Consolidated Standards of Reporting Trials
CRF	case report form
CRO	contract research organization
CRU	clinical research unit
CSR	Clinical Study Report
CT	clinical trial
CYP	cytochrome P450
DDI	drug-drug interaction
DILI	drug-induced liver injury
DMC	data monitoring committee
DNA	deoxyribonucleic acid
DPP-4i	dipeptidyl peptidase-4 inhibitors
DU	dispensable unit
EC	ethics committee
ECG	electrocardiogram
eCRF	electronic case report form

Abbreviation	Term
EDP	exposure during pregnancy
EFD	embryo-fetal developmental
eGFR	estimated glomerular filtration rate
EMA	European Medicines Agency
ET	early termination
EU	European Union
EudraCT	European Clinical Trials Database
CCI	
FSBG	fingerstick blood glucose
FSH	follicle-stimulating hormone
FT4	free thyroxine
GCP	Good Clinical Practice
GGT	gamma-glutamyl transferase
GLP-1	glucagon-like peptide-1
GLP-1R	glucagon-like peptide-1 receptor
HAE	hypoglycemic adverse event
HbA1c	hemoglobin A1c
HCVAb	hepatitis C antibody
HepBcAb	hepatitis B core antibody
HepBsAg	hepatitis B surface antigen
HIPAA	Health Insurance Portability and Accountability Act
HIV	human immunodeficiency virus
CCI	
HR	heart rate
HRT	hormone replacement therapy
IB	Investigator's Brochure
ICD	informed consent document
ICH	International Council for Harmonisation
ID	identification
IND	Investigational New Drug
INR	international normalized ratio
IP Manual	investigational product manual
IPAL	Investigational Product Accountability Log
IRB	Institutional Review Board
IRT	Interactive Response Technology
IV	intravenous
IVGTT	intravenous glucose tolerance test
IWR	interactive Web-based response
K ₂ EDTA	dipotassium edetic acid (ethylenediaminetetraacetic acid)
LBBB	left bundle branch block

Abbreviation	Term
LFT	liver function test
MATE	multidrug and toxin extrusion protein
MCH	mean corpuscular hemoglobin
MCHC	mean corpuscular hemoglobin concentration
MCV	mean corpuscular volume
CCI	[REDACTED]
MDR1	multidrug resistance mutation
MEN2	multiple endocrine neoplasia syndrome type 2
MMTT	mixed-meal tolerance test
msec	millisecond
MTC	medullary thyroid carcinoma
N/A	not applicable
NOAEL	no observed adverse effect level
OAT	organic anion transporter
OATP	organic anion transporting polypeptide
OCT	organic cation transporter
PD	pharmacodynamic(s)
pH	potential of hydrogen
PI	principal investigator
PK	pharmacokinetic(s)
PR	pulse rate
PT	prothrombin time
PVC	premature ventricular contraction/complex
QTc	corrected QT interval
QTcF	corrected QT using Fridericia's formula
qual	qualitative
RBC	red blood cell
RNA	ribonucleic acid
SAE	serious adverse event
SAP	Statistical Analysis Plan
SD	standard deviation
SGLT2	sodium glucose cotransporter 2
SOA	schedule of activities
SOP	standard operating procedure
SRSD	single reference safety document
ss	steady-state
SSID	single subject identifier
SUSAR	Suspected Unexpected Serious Adverse Reaction
t _½	Terminal phase half-life
T2DM	type 2 diabetes mellitus
TBA	total bile acids
TBili	total bilirubin

Abbreviation	Term
TEAE	treatment-emergent adverse event
T _{max}	time to reach C _{max}
TSH	thyroid stimulating hormone
UGT	uridine 5'-diphospho-glucuronosyltransferase
ULN	upper limit of normal
US	United States
WBC	white blood cell
WOCBP	woman of childbearing potential

1. VERSION HISTORY

Table 1. Summary of Changes

Version/ Date	Associated Protocol Amendment	Rationale	Specific Changes
1 21 Aug 2020	Original 30 Jun 2020	N/A	N/A
2 06 Apr 2021	Original 30 Jun 2020	CCI [REDACTED]	[REDACTED] [REDACTED] CCI [REDACTED] [REDACTED] [REDACTED] [REDACTED]
	Updated the analysis based on the blinded data review		Delete the recurrence analysis from Section 6.1.1.2.
	Clarified the details		Add the following sentences in Section 6.1.1.3. To calculate the percentage each week, the total number of participants who had not discontinued from the treatment prior to that respective week will be the denominator (note: if a participant did discontinue from the treatment during that respective week, they would be included in the denominator).

		
“Study Week” will be calculated using actual visit dates, rather than calendar days. For example, if vomiting occurs on Day 8 and Visit 2 occurs on Day 9 for a given patient, then the vomiting is considered to have occurred on Week 1 for this patient (Week 1 is Day1 to Day 8 for this patient).
 
CCI [REDACTED] [REDACTED] [REDACTED]

	Clarified the details	
Add the following sentence in Section 6.5.5.
 
“Study Week” will be calculated using actual visit dates, rather than calendar days. For example, if vomiting occurs on Day 8 and Visit 2 occurs on Day 9 for a given patient, then the vomiting is considered to have occurred on Week 1 for this patient (Week 1 is Day1 to Day 8 for this patient).

2. INTRODUCTION

This statistical analysis plan (SAP) provides the detailed methodology for summary and statistical analyses of the data collected in Study C3421015. This document may modify the plans outlined in the protocol; however, any major modifications of the primary endpoint definition or its analysis will also be reflected in a protocol amendment.

2.1. Study Objectives, Endpoints, and Estimands

There are no estimands in this study. Analysis population and methods to manage missing data are shown in Section 4 and Section 5.3, respectively.

Objectives	Endpoints
Primary:	Primary:

 To evaluate the safety and tolerability of multiple, oral doses of PF-06882961, administered to adult Japanese participants with T2DM. 	
 Incidence of treatment emergent AEs (AEs and SAEs), clinical laboratory abnormalities, vital signs and ECG parameters during the entire study.

2.2. Study Design

[figure not shown]
This is a Phase 1, randomized, double-blind (sponsor-open), placebo-controlled, 4-arm, parallel group study of PF-06882961 in adult Japanese participants with T2DM inadequately controlled on diet and exercise alone.

Participants will receive oral doses of PF-06882961 or placebo in this study. Approximately 9 participants will be enrolled in each arm, for a total of approximately 36 (4 arms) participants randomized. The randomization ratio will be 1:1:1:1 (1 of 3 active dosing regimens of PF-06882961 or placebo), and all 4 arms will be enrolled in parallel. The study will be conducted at a single clinical site in Japan.

Target dose levels, achieved after completion of titration, for the 4 arms of the study are placebo and PF-06882961 doses of 40 mg BID, 80 mg BID, and 120 mg BID. Dose titration will be incorporated to enhance tolerability to PF-06882961.

Following the screening period to confirm eligibility (up to 4 weeks), the treatment period will be approximately 8 weeks, followed by an approximate 4-week follow-up.

Figure 1. Schema of Study C3421015

3. ENDPOINTS AND BASELINE VARIABLES: DEFINITIONS AND CONVENTIONS

3.1. Primary Endpoint(s)

Incidence of treatment emergent AEs (AEs and SAEs), clinical laboratory abnormalities, vital signs and ECG parameters during the entire study.

3.1.1. Adverse Events

An adverse event is considered treatment emergent (TEAE) relative to a given treatment if:

- The event starts during the effective duration of treatment (i.e. starting after the first dose but before the last dose plus lag time)

The effective duration of treatment is determined by the lag time. Any event occurring within the lag time, whether this occurs during a break in treatment or at the end of treatment, is attributed to the corresponding treatment period. The lag time is defined by the Pfizer Standard of 365 days post last dose of study intervention.

A 3-tier approach will not be used to summarize TEAEs due to small sample size.

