8. STUDY ASSESSMENTS AND PROCEDURES

The investigator (or an appropriate delegate at the investigator site) must obtain a signed and dated ICD before performing any study-specific procedures.

Study procedures and their timing are summarized in the [SOA](#). Protocol waivers or exemptions are not allowed.

Safety issues should be discussed with the sponsor immediately upon occurrence or awareness to determine whether the participant should continue or discontinue study intervention.

Adherence to the study design requirements, including those specified in the [SOA](#), is essential and required for study conduct.

All screening evaluations must be completed and reviewed to confirm that potential participants meet all eligibility criteria. The investigator will maintain a screening log to record details of all participants screened and to confirm eligibility or record reasons for screening failure, as applicable.

Participants will be screened within 28 days prior to administration of the study intervention to confirm that they meet the study population criteria for the study. If the time between screening and dosing exceeds 28 days as a result of unexpected delays (eg, delayed drug shipment), then participants do not require rescreening if the laboratory results obtained prior to first dose administration meet eligibility criteria.

Every effort should be made to ensure that protocol-required tests and procedures are completed as described. However, it is anticipated that from time to time there may be circumstances outside the control of the investigator that may make it unfeasible to perform the test. In these cases, the investigator must take all steps necessary to ensure the safety and well-being of the participant. When a protocol-required test cannot be performed, the investigator will document the reason for the missed test and any corrective and preventive actions that he or she has taken to ensure that required processes are adhered to as soon as possible. The study team must be informed of these incidents in a timely manner.

For samples being collected and shipped, detailed collection, processing, storage, and shipment instructions and contact information will be provided to the investigator site prior to initiation of the study.

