8.3.1. Time Period and Frequency for Collecting AE and SAE Information

The time period for actively eliciting and collecting AEs and SAEs (“active collection period”) for each participant begins from the time the participant provides informed consent, which is obtained before the participant’s participation in the study (ie, before undergoing any study-related procedure and/or receiving study intervention), through and including a minimum of 28 calendar days, except as indicated below, after the last administration of the study intervention.

Follow-up by the investigator continues throughout and after the active collection period and until the AE or SAE or its sequelae resolve or stabilize at a level acceptable to the investigator and Pfizer concurs with that assessment.

For participants who are screen failures, the active collection period ends when screen failure status is determined.

If the participant withdraws from the study and also withdraws consent for the collection of future information, the active collection period ends when consent is withdrawn.

If a participant definitively discontinues or temporarily discontinues study intervention because of an AE or SAE, the AE or SAE must be recorded on the CRF and the SAE reported using the CT SAE Report Form.

Investigators are not obligated to actively seek AE or SAE after the participant has concluded study participation. However, if the investigator learns of any SAE, including a death, at any time after a participant has completed the study, and he/she considers the event to be reasonably related to the study intervention, the investigator must promptly report the SAE to Pfizer using the CT SAE Report Form.

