10.3.1. Definition of AE

AE Definition

• An AE is any untoward medical occurrence in a patient or clinical study participant, temporally associated with the use of study intervention, whether or not considered related to the study intervention.• NOTE: An AE can therefore be any unfavorable and unintended sign (including an abnormal laboratory finding), symptom, or disease (new or exacerbated) temporally associated with the use of study intervention.

Events Meeting the AE Definition

• Any abnormal laboratory test results (hematology, clinical chemistry, or urinalysis) or other safety assessments (eg, ECG, radiological scans, vital sign measurements), including those that worsen from baseline, considered clinically significant in the medical and scientific judgment of the investigator. Any abnormal laboratory test results that meet any of the conditions below must be recorded as an AE:
• Is associated with accompanying symptoms;• Requires additional diagnostic testing or medical/surgical intervention;• Leads to a change in study dosing (outside of any protocol-specified dose adjustments) or discontinuation from the study, significant additional concomitant drug treatment, or other therapy.• Exacerbation of a chronic or intermittent preexisting condition including either an increase in frequency and/or intensity of the condition.• New conditions detected or diagnosed after study intervention administration even though it may have been present before the start of the study.• Signs, symptoms, or the clinical sequelae of a suspected drug-drug interaction.• Signs, symptoms, or the clinical sequelae of a suspected overdose of either study intervention or a concomitant medication. Overdose per se will not be reported as an AE/SAE unless it is an intentional overdose taken with possible suicidal/self-harming intent. Such overdoses should be reported regardless of sequelae.

Events NOT Meeting the AE Definition

- Any clinically significant abnormal laboratory findings or other abnormal safety assessments which are associated with the underlying disease, unless judged by the investigator to be more severe than expected for the participant's condition.
- The disease/disorder being studied or expected progression, signs, or symptoms of the disease/disorder being studied, unless more severe than expected for the participant's condition.

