- Medical or surgical procedure (eg, endoscopy, appendectomy): the condition that leads to the procedure is the AE.
- Situations in which an untoward medical occurrence did not occur (social and/or convenience admission to a hospital).
- Anticipated day-to-day fluctuations of preexisting disease(s) or condition(s) present or detected at the start of the study that do not worsen.

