- If the investigator does not know whether or not the study intervention caused the event, then the event will be handled as “related to study intervention” for reporting purposes, as defined by the sponsor. In addition, if the investigator determines that an SAE is associated with study procedures, the investigator must record this causal relationship in the source documents and CRF, and report such an assessment in the dedicated section of the CT SAE Report Form and in accordance with the SAE reporting requirements.

Follow-up of AEs and SAEs

- The investigator is obligated to perform or arrange for the conduct of supplemental measurements and/or evaluations as medically indicated or as requested by the sponsor to elucidate the nature and/or causality of the AE or SAE as fully as possible. This may include additional laboratory tests or investigations, histopathological examinations, or consultation with other healthcare providers.
- If a participant dies during participation in the study or during a recognized follow-up period, the investigator will provide Pfizer Safety with a copy of any postmortem findings including histopathology.
- New or updated information will be recorded in the originally completed CRF.
- The investigator will submit any updated SAE data to the sponsor within 24 hours of receipt of the information.

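### The SAP's TEAE definition tests start date only, so an AE open at first dose that worsens on treatment can drop out of the TEAE tables, depending on how the site records it

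*SAP*

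**What the plan says.** SAP 3.1.1 gives a single criterion for a treatment-emergent AE: "The event starts during the effective duration of treatment (i.e. starting after the first dose but before the last dose plus lag time". The window closes late ("The lag time is defined by the Pfizer Standard of 365 days post last dose of study intervention"), but that concerns its end and not its beginning. No legible part of the SAP adds a criterion for an event that starts earlier and worsens.

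The primary endpoint in SAP 3.1 is "Incidence of treatment emergent AEs (AEs and SAEs), clinical laboratory abnormalities, vital signs and ECG parameters during the entire study". SAP 6.1.1 builds its incidence and severity tables on TEAEs and otherwise defers to sponsor reporting standards, which are not reproduced.

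Four protocol provisions bear on the point:

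- Section 8.3.1: AE collection "begins from the time the participant provides informed consent".
- Section 8: "Participants will be screened within 28 days prior to administration of the study intervention", so the pre-dose window can last up to four weeks.
- Section 10.3.1: the events that meet the AE definition include "Exacerbation of a chronic or intermittent preexisting condition including either an increase in frequency and/or intensity of the condition".
- Section 10.3.3, under follow-up of AEs and SAEs: "New or updated information will be recorded in the originally completed CRF". The same section has the investigator assign each AE to one intensity category.

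**The concern.** In a first look at tolerability in a new population, an increase in severity on drug is part of what the study is meant to detect. A rule that looks only at start date cannot see it when the AE record was opened before dosing. The error runs one way: the rule can leave on-treatment worsening out of the TEAE counts, but it cannot add any. The TEAE tables would then make the regimen look somewhat better tolerated than it was, both in which events appear and in their recorded severity.

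The pre-dose period offers some opportunity for such records. It runs from consent through an inpatient stay that includes a mixed-meal test on Day -1 (Protocol, Schedule of Activities, Table 2).

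**Working it through.** The plan states no figure for this point, so there is nothing to reproduce. The check is mainly a reading of the rules side by side, followed by arithmetic for scale.

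**Step 1. Can AE records with a pre-dose start exist?** Yes. Collection starts at consent and dosing may follow up to 28 days later.

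**Step 2. What happens to such a record under SAP 3.1.1?** It depends on how the event is entered:

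| Course of the event | How it is recorded | Start date tested | TEAE? |
|---|---|---|---|
| Resolves before dosing, recurs on treatment | New record | After first dose | Yes |
| Open at first dose, worsens on treatment | New record with its own onset | After first dose | Yes |
| Open at first dose, worsens on treatment | Original record updated | Before first dose | No |

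Only the third row loses the event.

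**Step 3. Which recording rule applies?** Protocol 10.3.1 treats exacerbation of a chronic or intermittent preexisting condition as an AE, which favours a new record. The list of what is not an AE agrees with this, since it removes only "Anticipated day-to-day fluctuations of preexisting disease(s) or condition(s) present or detected at the start of the study that do not worsen". Protocol 10.3.3 sends updated information to the record already made, which favours an update. An acute complaint that first arises after consent is not clearly a chronic or intermittent preexisting condition, so for that case the only recording instruction on the page is the one in 10.3.3. Each AE receives one intensity category, and nothing in the documents describes a dated change of severity within a record. An updated record could therefore carry the higher severity with a pre-dose start.

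**Step 4. Size of one omission.** The shift in incidence is 1/n, with n from Protocol 4.1 (about 9 per arm, about 36 in all, hence 3 × 9 = 27 on active drug):

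- one arm: 1/9 = 11.1 percentage points
- all active arms: 1/27 = 3.7 points
- all participants: 1/36 = 2.8 points

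For a preferred term, the shift applies if the participant has no other TEAE with that term. For any-TEAE incidence, it applies only if the participant has no other TEAE at all. In the completed 28-day T2DM study (Protocol 2.2.2.1) there were 319 TEAEs among 98 participants, an average of 319/98 = 3.3 each, so many affected participants would still be counted in the any-TEAE row.

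**Step 5. How likely is at least one case?** The documents give no rate. Let q be an assumed proportion of participants with a pre-dose AE that is open at first dose and worsens. The chance of at least one among n is 1 − (1 − q)^n:

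| Assumed q | n = 36 | n = 9 |
|---|---|---|
| 1% | 30% | 9% |
| 3% | 67% | 24% |
| 5% | 84% | 37% |
| 10% | 98% | 61% |

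These are chances that the situation arises, not that an event is lost. Loss also requires that the site updates the original record.

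**The case against.** The best reply is that the exclusion is inferred and not stated. The sentence in Protocol 10.3.3 about the originally completed CRF sits among follow-up instructions, beside postmortem findings and SAE updates. It does not say that a post-dose worsening is the same event, or that a pre-dose start date must be kept. Section 10.3.1 also ties an AE to the use of study intervention, so a complaint present before first dose could be read as preexisting and its exacerbation as a new AE. The sponsor reporting standards and CRF completion guidance, neither of which is available, may settle the matter. All of this stands, and it is why the point is that events can be lost, not that they are.

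A reader might infer more: that these events are excluded from the primary endpoint outright. The documents do not support that. The laboratory, vital-sign and ECG components have their own Day -1 baselines (SAP 3.1.2 to 3.1.4) and do not pass through the TEAE rule. SAP 6.1.1.3 summarizes nausea, vomiting and diarrhea by week, under a heading that refers to ongoing events, and is not worded as limited to TEAEs. SAP 6.1.1.2 lists these same AEs. That second view covers only three terms, however, and its weekly percentages are not described by severity, so it does not replace the TEAE tables.

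A reader might also infer that such cases are frequent because gastrointestinal complaints are common before treatment. The documents give on-study TEAE rates only, and exclusion criterion 1 removes clinically significant gastrointestinal disease.

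**Conclusion.** The gap is real and narrow. The TEAE definition has no worsening criterion, and for an acute AE that begins between consent and first dose and is still open at dosing, the documents do not say whether an increase in severity becomes a new record. Whether it enters the TEAE incidence and severity tables therefore depends on an unstated recording convention.

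The effect is confined to the TEAE component of the primary endpoint and can only lower its counts. How many participants are affected cannot be derived; the frequencies shown are illustrations from assumed rates. Because the analysis is descriptive (SAP 5.1), no error rate or power is affected. The change is still worth making: with arms of about 9, a single case is visible in a preferred-term row, and the remedy is short.

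**What to change.** Add a second limb to the definition in SAP 3.1.1: *or the event started before the first dose and increased in severity or became serious after it.*

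Add a counting rule so that the two routes cannot both apply: where the worsening already has its own AE record with a post-dose onset, count that record and do not also promote the original. Without this, one worsening could be counted twice.

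The cost is a sentence or two in the SAP and a small programming and data-review task: every pre-dose AE record open at first dose must be checked for a dated change in severity. The documents do not show that the CRF captures that date, so a site query may be needed where it is missing. SAP version 2 already reflects a blinded data review, so a new recording instruction to sites may come too late for some records. The SAP clause should therefore work on records as they were entered.
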